## **Introduction**

Joint arthroplasty (JA) is a safe and cost-effective musculoskeletal surgical procedure for relieving pain and improving function and health-related quality of life for patients with end-stage joint disease. As one of the most commonly performed procedures, more than 1.5 million knee arthroplasties (KA), more than 1 million hip arthroplasties (HA) and over 100 thousand shoulder arthroplasties (SA) were performed annually worldwide. In addition, more than 10 thousand elbow arthroplasties (EA) in Germany and has been rapidly increasing. Moreover, the incidence of ankle osteoarthritis has been estimated to be 47.7/100,000, affecting approximately 1% of the world population. The increased demands of JA pose a challenge for the health care system from a quality and finance perspective.

China is the most populated country in the world, and now has the second-largest economy in the world. As nearly 420 million Chinese are aged more than 50 years, and the living standards and health system continue to improve, the demand for healthcare, including JA, is increasing. However, the consequences of increased access to new medical technologies and their application to patient care is unknown. Description of epidemiological characteristics, risk factors, complications and resource utilization of JA, can provide valuable information for healthcare planners in China and similar countries, and can guide care providers to develop effective and targeted preventive measures to minimize mortality from this procedure.

Therefore, in this study, investigators will use data from a mandatory patient-level

national database, i.e., the Hospital Quality Monitoring System (HQMS), to study the epidemiological characteristics, risk factors, complications and resource utilization of JA (i.e., KA, HA, SA, EA and ankle arthroplasty [AA]).

## **Methods**

### **Data source**

This nationwide retrospective study will be a review of the HQMS database. The HQMS database is a mandatory electronic inpatient database system developed by the National Health Commission of the People's Republic of China. Since 2013, tertiary hospitals have been required to upload their inpatient discharge records. By 2019, the HQMS database has included about 230 million standardized inpatient discharge records of more than 1,000 hospitals across all 31 provincial-level administrative regions in mainland China. Patient demographics, clinical diagnosis, procedures and operations, costs and complications are all recorded in the HQMS database. The diagnosis is coded in the form of International Classification of Diseases, Tenth Revision (ICD-10), and the procedures and operations are coded in accordance with International Classification of Diseases, Ninth Revision, Clinical Modification (ICD-9-CM). A more detailed description of this database can be found in previous studies. This study was authorized by the HQMS Committee Board and approved by the institutional review board, with waiver of informed consent.

### **Study population**

Patients who were recorded in HQMS and underwent KA, HA, SA, EA and AA will be included in our study. Investigators will identify KA, HA, SA, EA and AA in HQMS based on the ICD-9-CM. To minimize the possibility of miscoding, other knee-related procedure, diagnosis codes and free texts will be also identified. Investigators will exclude: 1. Patients who didn't undergo these five types of JA; 2. Patients with missing demographics or medical data.

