### **Measurement of outcomes**

Five types of JA of our interest will be identified in HQMS, including KA, HA, SA, EA and AA. Epidemiological characteristics, risk factors, complications and resource utilization of these five types of JA will be analyzed.

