## **Statistical analysis**

Line charts will be drawn to describe annual change in trends of JA. Basic information in different groups will be compared. For continuous variables, Mann-Whitney U test will be used for non-normally variables and Student t-test will be used for normally variables, while chi-square test or Fisher's exact test will be used for categorical data. Then, multivariable-adjusted logistic regression will be performed to examine the risk factors of complications following JA (e.g., year of surgery, patient demographics and region of hospitals) with the calculation of odds ratios (ORs) and 95% confidence interval (CI). To minimize the effect of potential confounders, the propensity-score matching or multivariable-adjusted regression will be performed to compare the incidence of complications and resource utilization in different groups.

SAS 9.4 (SAS Institute Inc., Cary, NC, USA) will be used in all statistical analyses and  $P < 0.05$  will be considered as significant.

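### Repeat arthroplasty admissions of the same person are neither removed nor accounted for, so confidence intervals are likely to be somewhat too narrow

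*Combined protocol and SAP*

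**What the plan says.** In the combined protocol and SAP, the Study population section sets inclusion in terms of people: "Patients who were recorded in HQMS and underwent KA, HA, SA, EA and AA will be included in our study". Its two exclusions are also worded by person: "Patients who didn't undergo these five types of JA; 2. Patients with missing demographics or medical data". Neither removes a second or third arthroplasty admission.

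The Data source section describes a different unit. By 2019 the database held "about 230 million standardized inpatient discharge records of more than 1,000 hospitals", and records have been accumulating over several years: "Since 2013, tertiary hospitals have been required to upload their inpatient discharge records". The Introduction calls the same source patient-level ("investigators will use data from a mandatory patient-level"), but no section mentions a patient identifier or linkage between admissions.

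The Measurement of outcomes section says only that "Epidemiological characteristics, risk factors, complications and resource utilization of these five types of JA will be analyzed". It does not say whether a complication is counted per patient, per admission or per operation.

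The Statistical analysis section plans t, Mann-Whitney, chi-square and Fisher tests. It then states that "multivariable-adjusted logistic regression will be performed to examine the risk factors of complications following JA (e.g., year of surgery, patient demographics and region of hospitals", among other factors, will be studied. Nothing there deals with correlated records.

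**The concern.** A person who has one knee replaced, later the other, and then a hip meets the inclusion criterion through three discharge records. The plan does not say whether that person is one row or three.

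If there are three rows, the standard tests and ordinary logistic regression treat them as three unrelated people. Outcomes within a person are likely to be positively correlated, because frailty, comorbidity and often the hospital carry over. Standard errors for characteristics that stay fixed within a person are then too small. In a national data set judged against a single threshold of P < 0.05, weak associations would be declared significant slightly more often than the plan claims.

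If there is one row, the person has no single year of surgery, age or hospital region, and a complication outcome could accumulate over operations. What is at stake is the honesty of the intervals in the first case and of the odds ratios themselves in the second.

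**Working it through.** The plan states no sample size, complication rate, repeat-operation rate or within-patient correlation, so there is no figure of its own to reproduce. Every rate below is an assumption. The 0.05 threshold comes from the Statistical analysis section, which does not state sidedness; two-sided is assumed.

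**Which row does the plan imply?** The inclusion and exclusion criteria name patients. Year of surgery and hospital region in the regression, and charts of annual trends in arthroplasty, are attributes of an admission. The second group fits one row per admission better, because a patient with several operations has no single value for year.

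**One row per admission: bias.** Let p be the complication risk per operation and s the share of patients with two operations.

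- Pooled risk per admission = [(1−s)p + 2sp] / (1+s) = p(1+s)/(1+s) = p.
- The result does not depend on s, so a factor with no effect per operation has an odds ratio of 1.00 whatever the repeat rates.

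**One row per admission: variance.** Let m be the number of records per patient. Then design effect = 1 + (E[m²]/E[m] − 1) × ICC, with E[m] = 1+s and E[m²] = (1−s) + 4s. Actual alpha = 2 × [1 − Φ(1.96/√design effect)].

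- s = 0.10: E[m²]/E[m] = 1.3/1.1 = 1.1818. With ICC 0.01, design effect = 1 + 0.1818 × 0.01 = 1.0018, standard-error factor 1.0009, alpha 0.0502.
- s = 0.20: 1.6/1.2 = 1.3333. With ICC 0.1, design effect = 1.0333, factor 1.0165, alpha 0.0538.
- s = 0.30: 1.9/1.3 = 1.4615. With ICC 0.3, design effect = 1 + 0.4615 × 0.3 = 1.1385, factor 1.067, alpha 0.0662.

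This formula applies to factors that are constant within a person, such as sex. For a factor that changes between a person's admissions, such as year, the inflation is smaller.

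**One row per patient, complications collapsed to any complication.** Per-patient risk = (1−s)p + s[1−(1−p)²]. With p = 0.02, two operations give 1 − 0.98² = 0.0396.

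| Share with two operations | Per-patient risk |
|---|---|
| 0 | 0.0200 |
| 0.05 | 0.02098 |
| 0.10 | 0.02196 |
| 0.20 | 0.02392 |

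- 10% versus 5%: (0.02196/0.97804) / (0.02098/0.97902) = 1.05.
- 20% versus 0%: (0.02392/0.97608) / (0.0200/0.9800) = 1.20.
- Equal shares in both groups: 1.00.

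A spurious odds ratio therefore needs two conditions together: complications aggregated over a person's operations, and repeat rates that differ by level of the factor.

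**The case against.** A reader might infer that the plan, by selecting patients, lets complication odds rise with the number of operations and so biases its risk-factor odds ratios. Calendar year would be the obvious case, since patients first operated on early have longer to return. The documents do not support that inference. Naming patients in an inclusion criterion does not define the row of analysis, and no section says complications will be aggregated per patient. The year-of-surgery covariate and the annual trend charts point to admissions instead. The early-versus-late contrast also needs a rule that appears nowhere: index each patient at the first operation and then count complications from later ones. Even under aggregation, equal repeat rates leave an odds ratio of 1.00.

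A second objection is that the effect on the more natural reading is small. That stands: at most of the assumed inputs alpha stays close to 0.05.

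A third is that within-patient methods may not be feasible. Patient-level can simply mean not aggregated, and the documents confirm no identifier usable across admissions or hospitals. This also stands, and makes part of the fix conditional.

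None of these objections answers the remaining gap: repeat admissions are possible over a multi-year, five-joint window, nothing in the plan removes them, and the stated methods ignore them.

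**Conclusion.** The point holds in a limited form. The plan selects people from a file of discharge records, has no rule for repeat arthroplasty admissions, and analyses rows as if independent. On the per-admission reading that its covariates suggest, odds ratios are not distorted by the number of operations, but intervals are somewhat too narrow. With 10% to 30% of patients contributing two records and an ICC of 0.01 to 0.3, the design effect is about 1.002 to 1.14. Standard errors are then understated by a factor of up to about 1.07, and the actual two-sided alpha is 0.050 to 0.066. That repeat admissions occur is a reasonable inference rather than something the documents state, and their frequency and correlation are assumed.

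Spurious odds ratios of about 1.05 to 1.20 are a conditional possibility only. They need per-patient aggregation and unequal repeat rates, and the documents establish neither. Stating the unit closes off that possibility.

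**What to change.** In Study population, make each admission with a qualifying knee, hip, shoulder, elbow or ankle arthroplasty the eligible and analysed unit, and state that complications, costs, age, year and hospital are those of that admission.

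In Statistical analysis, where a patient identifier is available:

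- use patient-clustered standard errors (robust or GEE) for the regression models;
- repeat the risk-factor models on each patient's first recorded admission as a sensitivity analysis.

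If no usable identifier exists, say so and list the unmodelled dependence between repeat admissions as a limitation.

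The cost is about one sentence in each of the two sections and a linkage step in data preparation. Intervals will be slightly wider. Linkage may be incomplete, in which case some dependence remains and some admissions labelled as first will not be.

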### **Study variables**

Patient demographics (e.g., age, sex, marital status and comorbidities), clinical diagnosis, procedures and operations, costs, complications and hospital characteristics will be all extracted from the HQMS database. Medical insurance, including Urban Employee-Based Medical Insurance (UEBMI), Urban Resident-Based Medical Insurance (URBMI) and New Cooperative Medical Scheme (NCMS), self-pay and others (e.g., commercial insurance) will be identified in our study. Preexisting comorbidities will be extracted. The Charlson Comorbidity Index (CCI) will be calculate and categorized. Investigators will also extract the indication for KA. Hospital characteristics, such as region, volume of surgery will be extracted.

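### Excluding every patient with missing data before any analysis restricts trends, incidences and models alike to complete records; incidence is biased if completeness depends on the outcome, and odds ratios can be.

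*Combined protocol and SAP*

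**What the plan says.** The second exclusion criterion in Study population removes "Patients with missing demographics or medical data". It acts on the cohort, so it applies before anything in Statistical analysis.

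The fields that could trigger it are those in Study variables: "Patient demographics (e.g., age, sex, marital status and comorbidities), clinical diagnosis, procedures and operations, costs, complications and hospital characteristics will be all extracted". Insurance type is also collected. The plan does not say which of these count as medical data, or whether one blank field is enough.

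Three kinds of analysis then use the remaining patients:

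- Trends: "Line charts will be drawn to describe annual change in trends of JA".
- Risk factors: "multivariable-adjusted logistic regression will be performed to examine the risk factors of complications following JA". Calendar year and hospital region are among the examples given.
- Group comparisons: "the propensity-score matching or multivariable-adjusted regression will be performed to compare the incidence of complications and resource utilization in different groups".

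Data source states that "Patient demographics, clinical diagnosis, procedures and operations, costs and complications are all recorded in the HQMS database". That says the fields exist. It does not say that every field is filled, and the exclusion itself expects gaps. No section mentions imputation, a count of exclusions or a missing-data sensitivity analysis.

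**The concern.** The rule makes every analysis a complete-record analysis, and each type of result is exposed differently.

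- **Counts and trends.** A procedure with, say, a blank marital status is not counted. If recording improves over the years, part of an apparent rise in volume is a rise in completeness.
- **Crude incidence.** This needs only the outcome and the group, yet a patient with both recorded is lost if any other triggering field is blank. If patients with complications have more or fewer gaps than others, incidence is distorted.
- **Odds ratios.** Region and year are named risk factors. The data come from more than 1,000 hospitals in 31 regions, uploading since 2013, so recording quality could plausibly vary along the axes being compared. A difference could be created, hidden or shrunk.

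Epidemiological characteristics, complications and their risk factors are stated aims, so the rule affects the main results.

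**Working it through.** **Inputs.** The documents give no missingness rate, complication rate, effect size or number of arthroplasties, so the plan has no figure to reproduce. All rates below are assumed. They show how the rule works, not how large the effect is in this database.

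**Formulas.** Let s(g,y) be the probability that a record is complete in group g (0 or 1) with outcome y (1 = complication). When completeness depends only on group and outcome:

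- OR in complete records = true OR × s11·s00 / (s10·s01), first index group, second outcome.
- Incidence in complete records, group g = p·s(g,1) / [p·s(g,1) + (1−p)·s(g,0)].

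The OR is therefore unbiased whenever s11·s00 = s10·s01. Incidence is unbiased only if s(g,1) = s(g,0).

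**Incidence, true value 3.0%.**

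- 90% complete with a complication, 95% without: 0.0270 / (0.0270 + 0.9215) = 2.85%.
- 80% and 95%: 0.0240 / (0.0240 + 0.9215) = 2.54%.
- 95% and 90% (complicated stays better documented): 0.0285 / (0.0285 + 0.8730) = 3.16%.

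**Odds ratios and incidences together.** Assumed population: two equal groups; one binary confounder with OR 2 and prevalence 30% and 40%; baseline risk 1%; true adjusted group OR 1.50. The true incidences are 0.7 × 1.000% + 0.3 × 1.980% = 1.29% and 0.6 × 1.493% + 0.4 × 2.941% = 2.07%. A logistic model was fitted to the exact expected cell counts.

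| Completeness depends on | s00 | s10 | s01 | s11 | Ratio | OR | Incidence, groups 0 / 1 |
|---|---|---|---|---|---|---|---|
| (a) group only | 0.95 | 0.80 | 0.95 | 0.80 | 1.00 | 1.50 | 1.29% / 2.07% |
| (b) outcome only | 0.95 | 0.95 | 0.80 | 0.80 | 1.00 | 1.50 | 1.09% / 1.75% |
| (c) both, multiplicatively | 0.95 | 0.80 | 0.8075 | 0.68 | 1.00 | 1.50 | 1.10% / 1.77% |
| (d) both, not multiplicatively | 0.95 | 0.90 | 0.90 | 0.70 | 0.82 | 1.23 | 1.23% / 1.62% |
| (e) one cell slightly lower | 0.95 | 0.95 | 0.95 | 0.90 | 0.95 | 1.42 | 1.29% / 1.97% |
| (f) strong | 0.98 | 0.95 | 0.90 | 0.50 | 0.57 | 0.86 | 1.19% / 1.10% |

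For example, in (d) 0.70 × 0.95 / (0.90 × 0.90) = 0.82, and 1.50 × 0.821 = 1.23. The ORs are the same at a 3% baseline risk. In (d) to (f), 92% to 96% of records are kept at the 1% baseline, so a small excluded share is no reassurance.

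**Trend.** If 10% of records are excluded in an early year and 5% in a late one, flat volume appears to rise by a factor of 0.95 / 0.90 = 1.056.

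**Records lost.** If k fields are each blank independently in 1% to 3% of records, the share excluded is 1 − 0.99^k to 1 − 0.97^k: 3.9% to 11.5% for four fields, 9.6% to 26% for ten.

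**What imputation does in (a) to (f), in large samples.** If the missing item is a covariate and completeness depends only on observed group and outcome, imputation that includes both restores OR 1.50 and 1.29% / 2.07% in every row. If the missing item is the complication itself, imputation gives the same results as exclusion, for example OR 1.23 in (d).

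**The case against.** The other side has five arguments.

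- **No evidence of material missingness.** Uploading is mandatory, and nothing in the documents shows many gaps or ties them to outcome or group. This stands. The point is a risk created by a stated rule, and bias has not been demonstrated.
- **Joint dependence is not enough.** A reader might infer that odds ratios are biased whenever completeness depends on both outcome and group. Row (c) shows otherwise. Only a departure from multiplicativity matters, and the documents do not say whether there is one.
- **Direction is unknown.** A reader might infer that reported incidence will be too low. The documents do not support a direction, since complicated stays may be better documented.
- **The adjustment set is not given.** Statistical analysis offers only examples, so it is an inference that the models need every extracted field at once. The number of fields that can be blank is also unknown: comorbidities may be derived from diagnosis codes, where an absent code usually reads as no disease. This limits the lost-records figures. It does not change the cohort-level effect of the rule.
- **Imputation is not a general cure.** It does not repair outcomes missing according to their own value. If a covariate's missingness depends on its own value but not on the outcome given the covariates, complete-case logistic regression is valid while missing-at-random imputation may not be. This stands, and it is why both results should be reported.

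None of this defends dropping a patient from counts or crude incidence because an unrelated field is blank.

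**Conclusion.** The concern holds as a weakness of a stated rule. The current wording restricts trends, crude incidences and adjusted analyses to complete records, and the plan has no means of showing whether this matters. Incidence is biased, upward or downward, if completeness depends on the outcome. Odds ratios are biased under the narrower condition s11·s00 ≠ s10·s01. The odds-ratio algebra further assumes that completeness depends only on group and outcome.

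Neither the presence nor the size of bias can be determined from the documents. The calculations support only the statement that modest, uneven gaps could move a true odds ratio of 1.50 to 1.42 or 1.23 while more than 90% of records are kept, and that other patterns with as many gaps or more would leave it unchanged. A finding that the results will be biased, or that imputation alone would put them right, goes beyond what the plan shows.

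**What to change.** Amend Study population and Statistical analysis as follows:

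1. Limit the second exclusion to records in which joint type or year of surgery cannot be established.
2. Keep all other identified arthroplasties in counts and trends, and all with a recorded outcome and group in crude incidence.
3. Report missingness by variable, group, year and outcome.
4. In the adjusted analyses, multiply impute missing covariates (PROC MI and PROC MIANALYZE, in the SAS already planned). Put the outcome, joint, year and hospital characteristics in the imputation model, together with any other variable that defines the groups compared. Show the complete-case result as a sensitivity analysis.
5. If complications or costs are themselves missing, omit those records from the analysis of that outcome only, and add a not-at-random sensitivity analysis.

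The cost is SAP wording and extra analysis time, with no new data collection. The price in assumptions is that covariates are missing at random given the recorded fields. That is not always weaker than what complete-case odds ratios need, so both sets of results should be published.

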### **Study variables**

Patient demographics (e.g., age, sex, marital status and comorbidities), clinical diagnosis, procedures and operations, costs, complications and hospital characteristics will be all extracted from the HQMS database. Medical insurance, including Urban Employee-Based Medical Insurance (UEBMI), Urban Resident-Based Medical Insurance (URBMI) and New Cooperative Medical Scheme (NCMS), self-pay and others (e.g., commercial insurance) will be identified in our study. Preexisting comorbidities will be extracted. The Charlson Comorbidity Index (CCI) will be calculate and categorized. Investigators will also extract the indication for KA. Hospital characteristics, such as region, volume of surgery will be extracted.

